While the evidence seems to support a relationship between a change in microbiota and NEC, there is no clear relationship between anemia or transfusion and NEC. There have been no studies evaluating the relationship between anemia or transfusion and a change in microbiota. That is the primary focus of this study.

Hypothesis:

Anemia will result in alteration of the stool microbiota. Transfusion will return microbiota to baseline. The specific alteration in microbiota with anemia may include: increase in *Proteobacteria*, decrease in *Firmicutes*, and/or decrease in microbiota diversity.

Primary Outcome:

- Change in microbiota with anemia

Secondary Outcome:

- Change in microbiota after transfusion

Inclusion Criteria:

- Preterm infants less than 32 weeks gestation at birth
- ≥ 7 days and <30 days on enrollment
- On minimum 100mL/kg enteral feeds

Exclusion Criteria:

- NEC prior to enrollment
- Prior surgery
- Major congenital anomalies
- Oxygen requirement with $\text{FiO}_2 > 50\%$

Methods:**Definitions:**

- Severe anemia will be defined as a hematocrit $< 25\%$.
- Anemia will be defined as a hematocrit ≥ 25 and $<30\%$.
- No anemia will be defined as a hematocrit $\geq 30\%$.

Hematocrit will be tested per patient's care team. In this unit, hematocrit is usually obtained every Monday, and sometimes more frequently.

Sample Collection:

- Collect stool samples weekly (Sunday, Monday, or Tuesday)
- Collect stool samples 1, 4, and 7 days post-transfusion
- Stool will continue to be collected until infants are 38 weeks corrected gestational age (CGA) or discharge (whichever is earlier).

Data Collection:

Hematocrit	Gestational Age
Birthweight	Apgars
Sex	Race
Singleton/Multiple	Age at stool collection and at hematocrit blood sampling
Iron supplementation	Type of feeds (breastmilk/formula feed)
Calorie fortification of feeds	Total days on antibiotics
Number of transfusions	Positive cultures
NEC	Indomethacin exposure

Groups:

Paired samples will be obtained from the same infants, one before and one after onset of anemia. Therefore, the patients will serve as their own controls.

Sample Analysis:

- Stool samples obtained while patient is on antibiotics will not be included in analysis since the microbiota is expected to be significantly changed with large populations wiped out. Stool samples obtained 5 days after completion of antibiotics will be included in analysis again since infants are expected to be recolonized by that time.

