- qRT-PCR of samples will be performed to quantify the major bacterial groups: *Proteobacteria*, *Firmicutes*, and *Bacteroides*.
- Next generation sequencing will be done for qualitative analysis and metagenomics profiling of bacteria

Informed Consent:

New admissions to the Parkland NICU will be screened for recruitment if their birth gestational age (OB assigned) is less than 32 weeks 0 days and if they are at least 7 days old.

- If they meet these two criteria, they will be screened to ensure they do not meet exclusion criteria.
- If they do not meet the exclusion criteria, then their feeds will be evaluated. If they are on at least 100mL/kg/day of enteral feeds, then they will be approached for recruitment. Infants that are not yet on 100mL/kg/day of enteral feeds will have their charts assessed daily until 29 days of life. If and when they achieve 100mL/kg/day of enteral feeds, they will be approached for recruitment. If an infant does not achieve 100mL/kg/day of enteral feeds before 30 days of life, they will not be approached for enrollment in this study.
- If an infant meets the above criteria, and once their parent/guardian/LAR provides consent, then stool collection will begin for that infant from the next available defecated diaper. In cases where the patients are not the PI's patients, the study team will inform all the physicians caring for the patients within the NICU about this research study and

once they approve for their patients' (infant's) parents/guardians/LARs to be approached for consenting purpose to enroll the infant into this study, the bedside nurse will check with the parents/guardians/LARs if they would like to be approached. Once they let the beside nurse know if they agree to be approached, the nurse would inform this to [name] (the PI) and [name] (study team) who will be responsible for recruitment of subjects and they would approach the patient's parent/guardian/LAR for consenting purposes.

Sample Size Calculation:

Group sample sizes of 194 achieve 80% power to detect an odds ratio of 1.500 in a design with 2 repeated measurements having a simple covariance structure when the proportion for group 2 is 0.4 and group 1 is 0.5. The alpha level is 0.05.

Statistical Analysis:

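### The 194 and its 80% power are a no-loss result, yet the protocol's own rules leave an unquantified share of enrolled infants without a usable before/after pair

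*Protocol*

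**What the plan says.** The Sample Size Calculation section of the protocol consists of one claim, "Group sample sizes of 194 achieve 80% power to detect an odds ratio of 1.500 in a design with 2 repeated measurements", with the conditions "having a simple covariance structure when the proportion for group 2 is 0.4 and group 1 is 0.5" and "The alpha level is 0.05". It gives no enrolment target, no expected evaluable fraction and no second size.

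The Groups paragraph under Methods describes an own-control design: "Paired samples will be obtained from the same infants, one before and one after onset of anemia".

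Four other provisions decide whether an enrolled infant can supply that pair:

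- **Eligibility.** The inclusion criteria cover gestation, age ("≥ 7 days and <30 days on enrollment") and feed volume. Neither they nor the exclusion criteria mention hematocrit, although no anemia is defined as 30% or above.
- **Antibiotics.** Under Sample Analysis, "Stool samples obtained while patient is on antibiotics will not be included in analysis"; samples count again from 5 days after the course ends.
- **End of collection.** Sampling stops at 38 weeks' corrected age, or at discharge if that comes first.
- **Start of collection.** Under Informed Consent, the first stool is the next one available after consent, so an earlier stool cannot be recovered.

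**The concern.** An infant enters the before/after contrast only if a usable stool exists on each side of anemia onset. An infant already below 30% at enrolment may have no before sample. An infant who never falls below 30% while on study has no after sample. An antibiotic course, or the end of collection, can remove what would otherwise have been one side of the pair. These losses follow from the design and are more than ordinary drop-out: becoming anemic during the collection window is itself a condition for being analysed.

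If 194 is read as the number to enrol, the analysed number will be smaller and the 80% will not be reached under the protocol's own model. A null result on the primary outcome could then be read as better powered than it was.

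**Working it through.** **Inputs from the Sample Size Calculation section:** proportions 0.5 and 0.4 (odds ratio (0.5/0.5)/(0.4/0.6) = 1.5), alpha 0.05, power 80%, 2 repeated measurements, simple covariance. Sidedness is not stated; two-sided reproduces the figure and one-sided does not (152.5 after halving). **Assumed here:** loss rates of 10% to 50%, and within-infant correlations, because the protocol gives neither.

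**Step 1. Reproduce 194.** Pooled two-proportion formula, mean proportion 0.45:

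n = [1.960·√(2·0.45·0.55) + 0.842·√(0.5·0.5 + 0.4·0.6)]² / 0.1² = [1.379 + 0.589]² / 0.01 = 387.3 observations per group.

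Dividing by 2 independent measurements gives 193.7, so 194. Power at 388 observations per group is 80.1%. The figure reproduces with zero loss, so no allowance is hidden in it.

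**Step 2. Power after losses, in the protocol's own model.** With loss d in each group, n = 2·194·(1 − d) observations per group, and power = Φ{[0.1·√n − 1.379]/0.7}. For d = 0.20, n = 310.4 and √n = 17.62, so power = Φ(0.547) = 70.8%.

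| Assumed loss | Infants left per group | Power |
|---|---|---|
| 0% | 194 | 80.1% |
| 10% | 175 | 75.8% |
| 20% | 155 | 70.8% |
| 30% | 136 | 65.0% |
| 40% | 116 | 58.3% |
| 50% | 97 | 50.8% |

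**Step 3. What these figures count.** The model supposes 194 × 2 groups × 2 measurements = 776 observations. With one before and one after sample each, 194 infants supply 194 × 2 = 388. The middle column above therefore cannot be relabelled as pairs.

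**Step 4. Power for pairs.** McNemar normal approximation, with difference δ = 0.1 and discordant proportion π = 0.4 + 0.5 − 2·p₁₁, where p₁₁ = 0.4·0.5 + ρ·√(0.24·0.25):

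power = Φ{[δ·√n − 1.960·√π] / √(π − δ²)}.

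At ρ = 0, π = 0.5 and 194 pairs give Φ{[1.393 − 1.386]/0.7} = 50.4%. The two-proportion formula with 194 observations per side gives 50.8%. At ρ = 0.5, π = 0.255 and 194 pairs give Φ{[1.393 − 0.990]/0.495} = 79.2%.

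| Assumed ρ | Pairs for 80% | 194 pairs, no loss | 10% loss | 20% loss | 30% loss |
|---|---|---|---|---|---|
| 0 | 391 | 50.4% | 46.3% | 42.1% | 37.6% |
| 0.5 | 198 | 79.2% | 74.8% | 69.7% | 63.9% |
| 0.6 | 160 | 87.2% | 83.5% | 78.9% | 73.3% |
| 0.7 | 121 | 94.6% | 92.2% | 88.9% | 84.5% |

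**The case against.** The protocol never says that 194 infants will be enrolled. It says that groups of that size achieve 80% power, and it sets no recruitment stop. It also reports no anemia incidence, antibiotic use or discharge timing. A reader might infer that many infants will be lost; the document does not support that word. The antibiotic rule removes samples, not infants. Sampling is weekly, with more stools on days 1, 4 and 7 after a transfusion, so one lost stool need not cost a side of the pair. All of this stands, which is why the losses are shown only as an assumed range.

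A reader might also infer that 194 enrolled infants must fall short of 80% under any formula. They need not: in a paired analysis with an assumed correlation of 0.7, a 30% loss still leaves 84.5%. But the protocol claims its 80% under simple covariance, and 194 reproduces only with the measurements treated as independent, so it takes no credit for such a correlation.

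Finally, the Statistical Analysis section plans between-group tests and an ANOVA comparing groups, where infants who never become anemic could contribute. That is fair, and it means such infants drop out of the own-control contrast rather than out of every analysis. The Groups paragraph, however, makes the own-control contrast the design.

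An unseen statistical analysis plan does not answer the point, because the size and power are fixed in the protocol.

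**Conclusion.** The point holds in a limited form. The 194 is exactly the no-loss result and is the only size given, while the protocol's own rules make some non-evaluable infants foreseeable. If 194 is the number enrolled (per group, as worded), power in the protocol's own model is about 76% at 10% loss, 65% at 30% and 51% at 50%. These loss rates are assumptions; the true share is unknown from the document.

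It would be tempting to read those figures as powers for 175, 136 or 97 pairs. They are not. At zero correlation, 194 pairs give about 50% to 51% before any loss, and 175 pairs about 46% to 47%. With an assumed correlation of 0.5, power is about 79% with no loss and 70% at 20% loss. The mismatch between a two-group calculation and an own-control design is a separate and larger problem, and adjusting 194 for losses would not cure it. Any corrected base figure would still need an evaluable fraction.

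**What to change.** In the Sample Size Calculation section:

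1. Say whether 194 means infants enrolled, infants per group or evaluable before/after pairs.
2. Recompute the base figure for the paired design, with the within-infant correlation stated and varied.
3. Restate the power at the number of evaluable pairs expected from the planned enrolment, over a range of evaluable fractions informed by unit data.
4. Track recruitment in evaluable pairs.

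Do not simply relabel 194 as evaluable pairs with 80% power: under simple covariance that would put a new error into the protocol.

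The cost is a short recalculation, some extraction of unit data to estimate the evaluable fraction, and revised wording. The stated power will probably become less favourable. No extra infants are needed if the power is restated and enrolment is left as planned.

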Descriptive analysis will use percentages, means, medians, and measures of variability to describe demographic data. Categorical factors will be evaluated using Chi-square or Fisher exact test between the groups. Continuous factors will be evaluated using Student's t-test or Mann-Whitney U test if the data is non-normal distributed between the groups. Repeated measurements will use analysis of variance (ANOVA) to compare groups. The statistical significance level will be 0.05 for all statistical tests.

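### The protocol's only defined groups are before/after samples from the same infants, but the tests it names between groups are for independent samples and none is stated to be paired

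*Protocol*

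**What the plan says.** The Groups section is the only place where the protocol says what is compared: "Paired samples will be obtained from the same infants, one before and one after onset of anemia". It concludes "Therefore, the patients will serve as their own controls". The primary outcome is the change in microbiota with anemia, and the secondary outcome is the change after transfusion.

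The Statistical Analysis section first describes demographic data and then assigns tests:

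- Categorical: "Categorical factors will be evaluated using Chi-square or Fisher exact test between the groups".
- Continuous: Student's t-test, or "Mann-Whitney U test if the data is non-normal distributed between the groups".
- Repeated: "Repeated measurements will use analysis of variance (ANOVA) to compare groups".

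No McNemar, paired t-test or signed-rank test is named. The ANOVA sentence mentions neither a subject effect nor a within-infant factor.

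The laboratory measures are largely quantitative. Under Sample Analysis, "qRT-PCR of samples will be performed to quantify the major bacterial groups"; the Hypothesis includes "decrease in microbiota diversity".

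**The concern.** Chi-square, Fisher exact and Mann-Whitney assume independent observations. Student's t-test could in principle be paired. Here, however, it is used between groups with Mann-Whitney as its non-normal alternative, which points to the two-sample form. An analyst who takes the groups from the Groups section and the tests from the Statistical Analysis section would run independent-sample tests on two samples from the same infant.

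The stake is power. An own-control design gains precision by removing stable differences between infants from the comparison. An unpaired test leaves those differences in the standard error, so a real change with anemia may be missed.

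**Working it through.** **Inputs from the protocol.** One before and one after sample per infant (Groups); 194 per group, proportions 0.5 and 0.4, two repeated measurements, simple covariance, 80% power, alpha 0.05 (Sample Size Calculation).

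**Assumed, because the protocol gives no figure.** Within-infant correlation ρ = 0, 0.3, 0.5, 0.7; a shift of 0.2 SD; a lognormal shape for the skewed case; two-sided testing; and 194 read as the number of pairs.

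**Step 1: the protocol's own figure.** For two independent groups,

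n = [1.96·√(2·0.45·0.55) + 0.8416·√(0.25 + 0.24)]² / 0.1² = 387.3, rounded up to 388.

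With two measurements per subject and zero correlation this becomes 388·(1 + 0)/2 = 194, as stated. So 194 reproduces, but as two separate groups each measured twice. It is used below only as a plausible number of pairs; whether it suits a paired design is a separate sample-size question.

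**Step 2: what an unpaired standard error does to pairs.** In SD units, the true SE of the mean difference is √(2(1−ρ)/194), while the two-sample test uses about √(2/194) = 0.1015. The SE is therefore overstated by 1/√(1−ρ): 1.00, 1.20, 1.41 and 1.83. Under no change, the actual two-sided error rate is 2·[1 − Φ(1.96/√(1−ρ))] = 5.0%, 1.9%, 0.6% and 0.03%. It falls below the nominal level and does not exceed it.

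**Step 3: power, normal data, shift 0.2 SD.**

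- Paired t ≈ Φ(0.2/√(2(1−ρ)/194) − 1.96). The ratios 1.970, 2.354, 2.786 and 3.596 give 50%, 65%, 80% and 95%.
- Student's t on the same pairs ≈ Φ[(0.2 − 1.96·0.1015)/√(2(1−ρ)/194)], about 50-51% at every ρ.

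Simulation with 20,000 trials per setting agrees: paired t 0.499, 0.651, 0.797, 0.949; Student's t 0.503, 0.502, 0.503, 0.507.

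**Step 4: skewed data.** The same normal pairs were exponentiated, so the shift and ρ hold on the log scale. Simulated power:

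| Test | ρ=0 | 0.3 | 0.5 | 0.7 |
|---|---|---|---|---|
| Mann-Whitney (unpaired) | 48% | 47% | 48% | 47% |
| Wilcoxon signed-rank | 43% | 57% | 70% | 89% |
| Paired t or repeated-measures ANOVA, raw scale | 34% | 41% | 51% | 69% |

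A paired t-test on log values returns the paired row of Step 3. At ρ = 0 Mann-Whitney is slightly better than signed-rank.

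**Step 5: the ANOVA sentence.** With exactly two measurements per infant, repeated-measures ANOVA is equivalent to the paired t-test (F = t²). On that reading the primary pair is handled properly. The serial samples differ: stool is taken weekly, extra samples at days 1, 4 and 7 exist only after a transfusion, antibiotic periods are excluded, and collection ends at a variable time. Infants therefore contribute unequal sets, which classical repeated-measures ANOVA does not accommodate. No size is put on this, because the protocol gives no sample-loss rates.

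**The case against.** The strongest reply is that the tests are not meant for the pairs. The factor sentences follow the description of demographic data, so factors may mean infant characteristics. The before/after samples are repeated measurements and would fall under the ANOVA sentence. Infants who never become anemic could form a distinct set for the unpaired tests. Naming rank tests and models can also be left to an SAP.

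Much of this stands. A reader might infer that the protocol prescribes unpaired tests for its primary comparison; the text does not go that far, because the ANOVA sentence can cover the pair. Three things remain:

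- Fixed characteristics such as sex or birthweight cannot differ between two samples from one infant. The factors reading therefore needs groups of distinct infants, and the Groups section defines none.
- The protocol is not silent on tests. It names them, and the only one it names for non-normal data is unpaired.
- The ANOVA sentence neither states a within-infant term nor says that it governs the primary comparison.

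Two other inferences are unsupported. Unpaired testing would not inflate false positives when ρ is positive. Nor can a power loss be claimed for a binary primary outcome: the sizing text applies "when the proportion for group 2 is 0.4 and group 1 is 0.5", but the protocol never says what that proportion measures. It is likewise not stated that infants with incomplete serial samples would be dropped.

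**Conclusion.** The concern holds as a mismatch of wording that should be fixed. The named tests do not match the only defined groups, and nothing says which sentence governs the own-control comparison.

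The loss arises only if the unpaired tests are used on the pairs. At an assumed ρ of 0.5 it is about 50% power against 80% for normal data, and 48% against 70% for rank tests on lognormal data. There is no loss at ρ = 0, and it grows with ρ. These figures depend on the assumed correlation, shift and distribution. If repeated-measures ANOVA governs, this loss does not arise for the single pair. What is left is the lack of a paired option for skewed data and the poor fit of plain ANOVA to unequal serial samples.

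**What to change.** Amend the Statistical Analysis section to assign tests by comparison:

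1. Before/after anemia in the same infant: a paired t-test (on log values if skewed) or Wilcoxon signed-rank for bacterial quantities and diversity; McNemar for any outcome analysed as binary, once such an outcome is defined.
2. Serial post-transfusion and weekly samples: a mixed model, or GEE clustered on infant, in place of plain ANOVA.
3. Chi-square, Fisher exact, Student's t and Mann-Whitney: only for comparisons of distinct infants, such as ever against never anemic, with those groups defined.

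The cost is wording. Standard software suffices, and no extra infants or data are needed. The change does not by itself secure the stated 80% power, which has to be settled with the sample-size calculation.

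### The antibiotic exclusion and end-of-collection rules leave gaps in the post-transfusion stool series, but the only method named for repeated measurements is ANOVA, which handles gaps poorly

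*Protocol*

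**What the plan says.** The Statistical Analysis section gives one sentence on longitudinal data: "Repeated measurements will use analysis of variance (ANOVA) to compare groups". It does not say which form of ANOVA is meant or how incomplete series are treated.

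The Methods section determines what those series will look like.

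- **Schedule.** Under Sample Collection: "Collect stool samples weekly (Sunday, Monday, or Tuesday", and in addition "Collect stool samples 1, 4, and 7 days post-transfusion".
- **Exclusion.** Under Sample Analysis: "Stool samples obtained while patient is on antibiotics will not be included in analysis". Eligibility then resumes: "Stool samples obtained 5 days after completion of antibiotics will be included in analysis again".
- **End of collection.** "Stool will continue to be collected until infants are 38 weeks corrected gestational age (CGA) or discharge (whichever is earlier".

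The post-transfusion stools serve the secondary outcome, "Change in microbiota after transfusion". The primary comparison is a within-infant pair of stools on either side of the onset of anemia.

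**The concern.** The protocol produces an unbalanced series by its own rules and assigns it a method built for balanced data. Neither common reading of ANOVA fits.

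- **Classical repeated-measures ANOVA** needs every time point. An infant with one excluded or missed stool leaves that analysis, and the infant's remaining eligible stools go too.
- **Ordinary ANOVA across stools** keeps them all but treats several stools from one infant as independent. That conflicts with a design in which each infant is its own control.

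At stake are efficiency and selection. Antibiotic courses close to a transfusion are probably more common in sicker infants, so requiring complete series would select on antibiotic exposure, and with it probably on illness. The effect falls mainly on the secondary outcome, though the change after transfusion is also one of the protocol's two stated purposes.

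**Working it through.** **The plan's own figure.** The protocol gives no rate of missing stools. Its only calculation is 194 per group for proportions 0.5 and 0.4, 80% power, alpha 0.05 and 2 repeated measurements. The standard two-sided formula for two proportions gives 388 observations per group, and 388/2 = 194 with uncorrelated measurements, so the figure reproduces. It concerns two measurements and a binary outcome, not the day 1/4/7 series, so the data loss below is not converted into power.

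**Which stools one course removes.** Let e be the last antibiotic day relative to transfusion (day 0). On the reading that a stool on day d counts again once d ≥ e + 5, and provided the course had begun by day d:

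- day 1 is lost if e ≥ −3
- day 4 is lost if e ≥ 0
- day 7 is lost if e ≥ 3

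With e = 0, eligibility resumes on day 5. Days 1 and 4 are lost and day 7 is valid. A course begun by day 1 that ends on day 3 or later removes all three.

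**How wide the window is.** Course lengths are assumed; the protocol gives none.

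| Assumed course | Start days that remove at least one stool | Remove one | Remove two | Remove all three |
|---|---|---|---|---|
| 2 days | −4 to 7 (12 start days) | 6 | 6 | 0 |
| 7 days | −9 to 7 (17 start days) | 6 | 6 | 5 (starts −3 to 1) |

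For 12 of 12 start days with the short course, and 12 of 17 with the long one, at least one post-transfusion stool stays eligible. Those are the stools that a complete-series analysis would discard needlessly.

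**End of collection.** An infant discharged, or reaching 38 weeks corrected age, on day 5 after transfusion has no day 7 stool.

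**Share of complete series.** Assume each time point is available with probability p, independently. With one reference stool plus days 1, 4 and 7, the complete share is p⁴; with the three post-transfusion stools alone it is p³.

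| p (assumed) | p⁴ | p³ |
|---|---|---|
| 0.95 | 0.81 | 0.86 |
| 0.90 | 0.66 | 0.73 |
| 0.80 | 0.41 | 0.51 |

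Independence is the pessimistic case here, because one course tends to remove neighbouring stools together. With fully clustered loss the complete share is p itself, so the four-point ranges are 81% to 95%, 66% to 90%, and 41% to 80%.

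**Direction of selection.** Illustration only; all rates are assumed. Let 30% of infants be sicker, and let antibiotics break 40% of sicker and 10% of healthier series. The sicker share among complete series is

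(0.30 × 0.60) / (0.30 × 0.60 + 0.70 × 0.90) = 0.18 / 0.81 = 22%.

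Now add losses from discharge:

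| Discharge loss, sicker / healthier | Sicker share among complete series |
|---|---|
| 0% / 20% | 0.18 / (0.18 + 0.504) = 26% |
| 5% / 35% | 0.171 / (0.171 + 0.4095) = 29.5% |
| 5% / 50% | 0.171 / (0.171 + 0.315) = 35% |

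The shift away from 30% can shrink, nearly vanish or reverse.

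**The case against.** **The protocol never says incomplete infants are dropped.** True. It names no form of ANOVA and no complete-series rule, and a separate analysis plan, not available here, may deal with missing data. Deletion is inferred from the standard form of the method. What remains is that the protocol does fix the method, and neither usual form suits the data its own rules will produce. That is a poor choice as stated, not merely a detail left for later.

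**The four-point series is a construction.** Also true. The protocol does not explicitly assign ANOVA to a day 1/4/7 profile, and the comparison it describes in most detail is a pair. If ANOVA were applied only to pairs, two stools per infant would suffice. But the three timed stools are scheduled, they are repeated measurements, and no other method is offered for them.

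**A reader might infer that the result would rest on the healthier infants.** The documents do not support that. It is plausible for the antibiotic rule alone. Discharge tends to come earliest for infants who recover sooner, so that rule may remove healthier infants, and the 38-week limit depends on age rather than illness.

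**A reader might also infer that one missed stool removes the infant from the study's analyses.** It does not. The infant leaves that repeated-measures analysis at most; the anemia pair and other comparisons using weekly stools can still stand.

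**A mixed model does not restore excluded stools.** Correct. Infants who lose all three post-transfusion stools still contribute nothing after transfusion, so the remedy brings efficiency and only partial relief from selection.

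**Conclusion.** The point holds as a mismatch between the named method and the data that the Methods section will generate. It should be corrected, but it bears mainly on the secondary outcome.

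The loss of individual stools follows directly from the protocol's rules. Its consequence in the analysis depends on the form of ANOVA: lost valid stools under the classical form, ignored within-infant correlation under the ordinary one. The complete-series shares of 81%, 66% and 41% rest on assumed availability and independent loss, and mark the low end of the range when loss is clustered. They show how much data could be lost and do not measure bias. Selection by antibiotic exposure is possible; its size and net direction cannot be determined from the protocol.

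**What to change.** Replace the sentence on repeated measurements with wording such as: *Repeated stool measurements will be analysed with a linear mixed model (a generalized linear mixed model for binary or count outcomes) with a random infant effect, including every eligible stool at its actual day of collection.* Keep the antibiotic exclusion as written.

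An infant who loses one or two stools to that rule then still contributes the rest. Age at stool collection is already on the data list, so actual timing can be used.

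The cost is one sentence and slightly more modelling work, with no change to collection or patients. The model relies on a missing-at-random assumption, which should be stated. Reporting how many infants have zero, one, two or three eligible post-transfusion stools would show how far the result still depends on who remained eligible.

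### The primary outcome names no measure, and the stated 80% power belongs to an unnamed yes/no event computed as two independent groups rather than as the paired comparison the design describes

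*Protocol*

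**What the plan says.** - **Primary Outcome:** "Change in microbiota with anemia". No variable, metric or threshold is attached. The Secondary Outcome, "Change in microbiota after transfusion", is worded in the same way.
- **Hypothesis:** "The specific alteration in microbiota with anemia may include: increase in *Proteobacteria*, decrease in *Firmicutes*, and/or decrease in microbiota diversity". None of the three is ranked above the others.
- **Groups:** "Paired samples will be obtained from the same infants, one before and one after onset of anemia". Each infant acts as its own control.
- **Sample Analysis:** "qRT-PCR of samples will be performed to quantify the major bacterial groups", with sequencing in addition.
- **Sample Size Calculation:** "Group sample sizes of 194 achieve 80% power to detect an odds ratio of 1.500", for proportions of 0.5 and 0.4, two repeated measurements and a simple covariance structure. "The alpha level is 0.05". The event behind the proportions is not identified.
- **Statistical Analysis:** "The statistical significance level will be 0.05 for all statistical tests". For repeated measurements the only method named is analysis of variance.

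**The concern.** Three parts of the protocol should describe the same quantity: the primary outcome, the powered comparison and the test that decides the primary question. Here they cannot be matched. The outcome names no measure. The power calculation uses a binary event that no section defines, while the laboratory work quantifies bacterial groups and analysis of variance suits a continuous measure. The calculation also treats the two conditions as independent groups, while the design pairs samples within infant.

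A reader therefore cannot tell which measure the 80% refers to, or whether it applies to the planned comparison at all. With three unranked changes and the same 0.05 for every test, the plan also does not say which result would support the primary conclusion. If one significant change out of three were taken as enough, 0.05 would be the level of each test and not of the conclusion.

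**Working it through.** **1. The protocol's own figure.** Inputs from Sample Size Calculation: p1 = 0.5, p2 = 0.4, alpha 0.05, power 80%, two measurements. The odds ratio is (0.5/0.5)/(0.4/0.6) = 1.5, as stated. The pooled two-proportion formula, two-sided, gives

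n = [1.960·√(2·0.45·0.55) + 0.842·√(0.5·0.5 + 0.4·0.6)]² / 0.1² = 387.3, so 388 observations per group.

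Simple covariance is read as zero correlation between the two measurements, so 388/2 = 194. The figure reproduces. A one-sided test gives 305/2 = 152.5, which does not match, so the full two-sided 0.05 was used for this one event.

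**2. The same proportions as a paired comparison.** Groups describes one sample on each side of anemia onset. So 194 infants supply 194 observations on each side, not 388. With within-infant correlation r, the discordant cells are 0.5·0.6 − r·√(0.5·0.5·0.4·0.6) and 0.4·0.5 − r·√(0.5·0.5·0.4·0.6), where the root equals 0.245. Their sum is D and their difference is 0.1. McNemar approximation:

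power = Φ{[0.1·√n − 1.960·√D] / √(D − 0.01)}

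The protocol gives no within-infant correlation beyond the zero read from its covariance statement, so r is an assumption.

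| r | Discordant cells | Power, 194 pairs | Infants for 80% |
|---|---|---|---|
| 0 | 0.300 / 0.200 | 50.4% | 391 |
| 0.3 | 0.227 / 0.127 | 65.2% | 275 |
| 0.5 | 0.178 / 0.078 | 79.2% | 198 |

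For r = 0: 0.1·√194 = 1.393, 1.960·√0.5 = 1.386, and the difference of 0.007 over 0.7 gives Φ(0.01) = 50.4%. With 194 pairs, 80% is reached at r of about 0.51. If 194 per group meant 388 infants each giving a pair, power is 79.8% at r = 0 and 91.5% at r = 0.3. These figures apply only to a binary measure.

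**3. Error rate if any one of three changes counted.** This is a condition, not a rule in the protocol. Each test is at two-sided 0.05.

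- Independent, either direction: 1 − 0.95³ = 14.3%.
- Independent, hypothesised direction only (0.025 per test): 1 − 0.975³ = 7.3%.
- Correlated: three normal statistics with common correlation c, integrated numerically over the shared factor t. For the hypothesised direction, 1 − ∫Φ[(1.960 − √c·t)/√(1 − c)]³ φ(t) dt. For either direction, the same with both tails removed. The values of c are assumed.

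| c | Either direction | Hypothesised direction |
|---|---|---|
| 0 | 14.3% | 7.3% |
| 0.5 | 12.5% | 6.3% |
| 0.7 | 10.9% | 5.5% |
| 0.9 | 8.4% | 4.2% |
| One test | 5% | 2.5% |

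The directional rate falls below 5% at c of about 0.79, but it stays above its own single-test benchmark of 2.5% at every value shown.

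**The case against.** The strongest reply is that the three changes describe expected biology and are not a success criterion. The stated hypothesis is a single claim, that anemia alters the microbiota, and one global test could address it. Rules for ordering or adjusting tests are commonly left to an SAP, which is not at hand. A significance level of 0.05 does not rule out adjustment, because adjusted p-values can also be compared with 0.05.

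Much of this stands. A reader might infer that the study has a 14.3% false positive rate. The protocol does not support that: it states no rule that any one change suffices, and the conditional rate runs from 14.3% down to 4.2% with the direction counted and the assumed correlation. The absence of a multiplicity procedure is likewise no fault in itself.

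A reader might also infer that the study has only 50% power. That holds only for a binary measure, 194 infants with one usable pair each, and zero within-infant correlation. For a continuous abundance or diversity measure the figure says nothing. The paired power problem is also separate from multiplicity. It belongs here because the powered event must be named before either can be settled.

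The reply does not reach the core. The primary measure and the powered event are undefined in the protocol's own outcome and sample size sections, and the calculation does not match the design in Groups.

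**Conclusion.** The point holds as a specification fault that should be corrected. Two parts rest on the text alone: no primary measure is named, and the 80% power refers to an unidentified binary event in two independent groups, not to the paired comparison described.

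The consequences are conditional. For a binary measure with 194 single pairs, power is about 50% to 79% over assumed correlations of 0 to 0.5. If 388 infants were meant, it is about 80% at zero correlation. For a continuous measure it is unknown. The error rate exceeds the single-test level only if any one of the three changes is accepted as support. The plan neither states nor excludes that reading. Confidence is medium, because an SAP not shown may settle the decision rule.

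**What to change.** - **Primary Outcome:** name one measure, chosen on scientific grounds, compared within infant before versus after anemia begins.
- **Sample Size Calculation:** say what the 0.5 and 0.4 count and whether 194 means infants or infants per group. Restate the power as a paired comparison of the named measure, with the assumed within-infant correlation shown. If the measure is continuous, a new calculation is needed. Where power falls short, state the lower figure rather than enrol more infants.
- **Statistical Analysis:** replace the blanket sentence with wording such as: *The primary measure, tested at two-sided 0.05, alone decides the primary conclusion. The other microbiota measures and the change after transfusion are secondary or supportive.* Holm adjustment of the secondary measures, or false discovery rate control for sequencing results, is optional and could sit in the SAP.

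The cost is wording in two sections and one restated calculation. The downsides are that the other measures lose a claim at the full 0.05 and that the stated power may become less favourable.
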